7.5 Risk adaptive approach

This study is following a risk-adaptive approach to safety reporting because the intervention being studied has already been proven to be safe and is already in use for PTSD.

7.6 Safety reporting period

Adverse events/reactions will be recorded and reported from the point of consent (baseline assessment) until the 12-month follow-up assessment or point of withdrawal from the study.

7.7 Identification of AEs

[figure not shown]
AEs are expected to occur throughout the course of the trial. Local researchers are responsible for recording AEs for their participants during the trial.

We anticipate that some AEs may be identified during EMDR appointments for participants allocated to the intervention. Up until the 52 week follow up, AEs may also be detected via researcher contact to encourage questionnaire completion, or via completion of study questionnaires (across both UC and EMDR groups). We will not actively monitor for events outside of study questionnaires. However, the central and/or local research team will report any AEs that occur should they become aware, as below.

[figure not shown]
We anticipate that most AEs will be identified via study questionnaires. For example, participants will be asked about suicidal thoughts as part of the PHQ-9 and BDI-II questionnaires, and about hospital treatment as part of the 26 week and 52 week questionnaires; their responses and other disclosures may lead to further investigation in relation to AE reporting. The central and/or local team will communicate with clinical PI and GP practices if additional information is required, e.g., to ascertain the nature and severity of an AE. If the study team become aware of an AE, they will assess and log this according to trial recording and reporting procedures; see below.

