6.7 Emergency contact procedure for participants

The participant's GP will retain clinical responsibility for them throughout their participation in the trial. Details of what a participant should do if they experience any problems or adverse effects whilst taking part in the trial is detailed in the PIL.

If a symptom is troublesome (as explained in the PIL) participants are advised to seek medical help in the normal way (e.g., dialling 111 or contacting their GP). In an emergency they should phone the emergency services or attend an Emergency Department. There will also be information provided about helplines participants can choose to access for mental health support 24/7, which will be available on the study website, or on paper if required.

Participants receiving EMDR will complete a measure of depressive symptoms (PHQ-9) for each session which will be shared with their therapist. This will completed via REDCap survey shortly ahead of the session, or completed in person at the beginning of each session. If this is completed on paper, the therapist will enter this into the database following the therapy session. A safety protocol outlines the procedure to follow if a therapist is concerned about the risk, such as increased suicidality. Further details on the safety protocol are outlined in section 7.1.

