7.2 Safety Definitions

Adverse Event

An adverse event (AE) is any untoward or undesirable medical occurrence in a subject receiving treatment according to the protocol. This includes occurrences which are not necessarily caused by or related to administration of the research procedures. An adverse event can therefore be any

unfavourable and unintended sign, symptom or disease temporally associated with the use of the intervention or research procedures whether or not considered to be related to the intervention/research procedures.

Adverse events that might be expected to occur at a higher rate in this group of participants include episodes of self-harm not requiring hospital admission and worsening of depression sufficient to require referral to a clinician. Although these AEs are expected, they will still be reported as data in this study. Variations in mood, including worsening of depression that does not lead to self-harm or hospitalisation, are commonly seen during therapy and would not be reported as individual adverse events. Expected events are listed in full in section 7.9.

There may be more AE reports in the intervention group as a result of their regular contact with the study team (i.e. receipt of up to 18 EMDR sessions with the study therapist, and more regular completion of the PHQ-9 and related participant safety risk assessments as part of therapy). This will be taken into consideration when interpreting the pattern of AEs.

Adverse Reaction

An adverse reaction (AR) is any undesirable experience that has happened to a subject that is suspected to be caused by the intervention.

Serious Adverse Event

A serious adverse event (SAE) is any adverse event which:

- results in death,
- is / was life threatening*,
- requires hospitalisation or prolongs an ongoing hospitalisation**,
- results in persistent or significant disability or incapacity,
- consists of a congenital anomaly or birth defect,

Other important medical events that may jeopardise the subject and may require medical or surgical intervention to prevent one of the outcomes listed above should also be classed as an SAE.

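### Adverse events are looked for more often in the EMDR arm, and no direct question on non-admission events is shown for both arms, so a raw comparison of these events is open to detection bias

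*Protocol*

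**What the plan says.** Section 7.7 describes two main ways of finding events. One is the EMDR appointment, which exists in one arm only. The other is the study questionnaires and the contacts made to encourage their completion, which exist in both. It expects the second to dominate: "We anticipate that most AEs will be identified via study questionnaires". It gives examples of what the questionnaires ask. One is hospital treatment, at the 26- and 52-week follow-ups only. The other concerns suicidality: "participants will be asked about suicidal thoughts as part of the PHQ-9 and BDI-II questionnaires". Beyond that, "We will not actively monitor for events outside of study questionnaires", although events that come to the team's notice are to be reported.

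The extra route in the EMDR arm is structured. Section 6.7 states: "Participants receiving EMDR will complete a measure of depressive symptoms (PHQ-9) for each session which will be shared with their therapist". Under section 7.1.1 the therapist assesses risk at the first session, repeats this when item 9 of the PHQ-9 or clinical concern calls for it, and must report incidents of serious harm to the study team.

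Section 7.9 lists expected events that will still be reported. Three of them need no admission: self-harm, suicide attempts, and worsening that requires referral to a clinician. Table 2 in section 6.8 itemises the assessments and has no adverse-event row.

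Section 7.2 acknowledges the consequence: "There may be more AE reports in the intervention group as a result of their regular contact with the study team". It repeats this for serious events and undertakes, in both places, to bear it in mind at interpretation.

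**The concern.** If one arm has more occasions on which an event can come to light, event counts differ between arms even when the true risks are equal. For events that both arms are asked about directly, the shared question limits the difference. For events that neither arm is shown to be asked about, reporting depends on disclosure, and EMDR participants have many more occasions to disclose.

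The harm data would then be hard to read in either direction. An excess in the EMDR arm could be put down to contact. Similar counts could hide a real difference if events were missed. Section 7.5 rests the light safety approach on use in PTSD, which is an exclusion here (section 5.6.1.2), so this trial is a natural source of harm evidence in depression. The DMC, asked in section 7.10 to look for patterns and trends, would work from the same counts.

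Analysis cannot fully repair this. A question never put to usual-care participants cannot be added later, and a route of identification not recorded at the time may be lost.

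**Working it through.** The protocol gives no adverse-event rate and no power for a harm comparison, so there is no stated figure to reproduce.

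**Contacts.** Follow-ups in both arms: 6, at 2, 8, 16, 26, 39 and 52 weeks (section 5.3). Planned EMDR sessions: 12-18 (section 5.7.1).
- Usual care: 6.
- EMDR: 6 + 12 = 18 (3.0 times as many) to 6 + 18 = 24 (4.0 times).

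**What the shared schedule covers.**
- Suicidal thoughts: PHQ-9 at all six follow-ups, BDI-II at 26 and 52 weeks.
- Hospital treatment: asked at 26 and 52 weeks.
- Self-harm, suicide attempts without admission, and worsening needing referral: no direct question shown. A question about suicidal thoughts does not ask about an act, and a hospital question misses events that did not reach hospital.

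**Possible size.** Let the true risk be equal in both arms. Let *c* be the probability that the common route finds an event, and *e* the probability that therapy sessions find an event the common route missed. Both are assumptions; the documents give neither.
- Observed usual-care risk = true risk × *c*.
- Observed EMDR risk = true risk × [1 − (1 − *c*)(1 − *e*)].
- Spurious risk ratio = [1 − (1 − *c*)(1 − *e*)] / *c*.

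For example, *c* = 0.3 and *e* = 0.6 give (1 − 0.7 × 0.4)/0.3 = 0.72/0.3 = 2.40.

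| *c* | *e* = 0.2 | *e* = 0.4 | *e* = 0.6 |
|---|---|---|---|
| 0.3 | 1.47 | 1.93 | 2.40 |
| 0.5 | 1.20 | 1.40 | 1.60 |
| 0.7 | 1.09 | 1.17 | 1.26 |
| 0.9 | 1.02 | 1.04 | 1.07 |

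With 190 per arm (380/2, no attrition) and an assumed true risk of 20%, the chance of a false significant excess in the EMDR arm at the 5% level is about 77% at *c* = 0.3, *e* = 0.6, and about 5% at *c* = 0.7, *e* = 0.2.

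**After restriction to a common route.** If every event reported through an identical item in both arms is counted, whether or not therapy had already found it, both arms are observed at true risk × *c*. The expected ratio is 1.00, provided therapy contact does not change how participants answer the item.

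**The case against.** The protocol offers more shared detection than the contact count suggests. It expects the questionnaires, which go to both arms, to find most events. From 8 weeks both arms also give a global rating of change and report other treatments (Table 2). Both report resource use at 26 and 52 weeks (section 6.16), and primary care records are extracted with consent. The researcher risk policy in section 7.1.2 applies to both arms and names recent self-harm as a trigger. The imbalance is openly disclosed, and how events are compared between arms could be left to the SAP. The items in section 7.7 are examples, and the questionnaires, the adverse-event form and the operating procedure are not shown.

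Much of this stands. A reader might infer that the arms share no safety question at all; section 7.7 shows that they do. A reader might also infer that the bias is beyond correction; it is not, because hospital events are asked about in both arms and a shared item would deal with most of the rest.

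A larger figure is also tempting. If every contact had the same independent 5-10% chance of disclosure, detection would be 27-47% in usual care and 60-92% with EMDR, a ratio of 1.8 to 2.7. The documents do not support that as an estimate. Events after therapy ends gain no extra sessions, early agreed endings are allowed (section 5.7.1), and 12-19% attended fewer than two sessions in the earlier psychotherapy trials cited in section 5.4. At 20% per contact and 12 sessions the same formula gives 0.982/0.738 = 1.33.

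What does not answer the point is the appeal to the SAP. An analysis plan can choose among recorded events but cannot create a question that was never asked. The other shared routes do not amount to a direct question on the events in section 7.9.

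**Conclusion.** The point holds as a design weakness that should be put right. Ascertainment is unequal by design, no direct question to both arms on the non-admission events is shown, and the only stated safeguard is an intention to consider the imbalance. A raw between-arm comparison of those events is open to detection bias against EMDR.

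The size is unknown. The range of about 1.0 to 2.4 rests on assumed detection probabilities and equal true risk. Bias is small where the common questionnaires catch events well, which probably includes hospital treatment, and can be large where they catch them poorly. Confidence is moderate: the unseen questionnaires or operating procedure may already contain a suitable item, in which case what remains is to show it in Table 2 and name the comparison that uses it.

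**What to change.** 1. Add one identical short item to the 8-, 16-, 26-, 39- and 52-week questionnaires in both arms, covering the events in section 7.9 and hospital admission, and show it as a row in Table 2.
2. State that the between-arm comparison of these events uses what is reported through that item, counting each such event whether or not therapy had already found it.
3. Record on the adverse-event form every route by which an event was identified, and report events found only in therapy separately.

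The form should not record the first route alone, with the comparison limited to events first found at common follow-ups. EMDR-arm events disclosed in therapy would drop out, while usual care could lose none. In the per-contact model above, with contacts in random order, the EMDR arm would keep 0.603 × 6/18 = 0.201 against 0.265 in usual care (ratio 0.76, at 5% and 12 sessions), or 0.920 × 6/24 = 0.230 against 0.469 (ratio 0.49, at 10% and 18 sessions). Equal risk would look like protection.

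The cost is an amendment, one item, one table row and a form field. Brief follow-ups become slightly longer. Asking directly about self-harm and suicide attempts will bring more disclosures to be handled under the existing researcher risk policy in section 7.1.2, and this needs staff time.

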7.8 Reporting overview

7.8.1 Adverse Events Overview

7.8.2 Serious Adverse Events Overview

*refers to the initial notification to University Hospitals Bristol and Weston NHS Foundation Trust (UHBW) on behalf of the Sponsor. All safety information, including information relating to safety events that are not subject to expedited reporting, will be closely monitored by the DMC throughout the trial. The DMC will be provided with a report at least annually (unless specified by the DMC).

7.9 Expected events

Expected events are clinical outcomes that routinely occur when delivering the intervention.

Expected AEs and SAEs that are a more common occurrence in this study population regardless of the study are listed below. Although these events are expected, they will still be reported in this study.

- Self-harm
- Self-harm leading to hospitalisation
- Suicide attempts
- Suicide attempts leading to hospitalisation
- Worsening of depression which requires referral to a clinician
- Worsening of depression leading to hospitalisation

All AEs will be assessed for seriousness, severity, causality and expectedness by a clinical PI or nominated deputy clinician. Relatedness to mental health will also be assessed. We will develop a detailed, study-specific standard operating procedure for reporting and recording adverse events in line with the Sponsor's requirements. This will be in place prior to the commencement of recruitment activities.

7.10 Responsibilities

Centre Clinical Principal Investigator:

- Will check individual reports of AEs and use medical judgement in assigning seriousness, severity, causality and whether the event/reaction was expected, and whether the event was related to the participants mental health. If the local Clinical PI is not available this role will be delegated to a deputy clinician, or clinical PI from another centre.
- Ensuring that all SAEs are recorded and reported to the sponsor within 24 hours of becoming aware of the event and provide further follow-up information as soon as available.
- Ensuring that AEs and ARs are recorded and reported to the sponsor in line with the requirements of the protocol.

Chief Investigator:

 Maintain oversight of the safety of participants in the trial, including an ongoing review of the risk/benefit. A clinical PI (or deputy) will provide clinical advice to the CI in this regard.

Sponsor:

University Hospitals Bristol and Weston NHS Foundation Trust (UHBW) will monitor safety information on behalf of the Sponsor. UHBW will be given the opportunity to review the trial AE reporting SOP prior to the start of the trial.

Trial Steering Committee (TSC):

In accordance with the Trial Terms of Reference for the TSC, the group will periodically review safety data and liaise with the DMC regarding safety issues.

Data Monitoring Committee (DMC):

In accordance with the Trial Terms of Reference for the DMC, group will periodically review overall safety data to determine patterns and trends of events, or to identify safety issues, which would not be apparent on an individual case basis.

The TSC and DMC will advise the trial team on the frequency of review of individual and cumulative SAEs.

7.11 Notification of deaths

All deaths will be reported to the Sponsor irrespective of whether the death is related to disease progression, the intervention, or an unrelated event.

7.12 Pregnancy reporting

We do not plan to report or follow-up pregnancies in this trial.

7.13 Urgent safety measures

The Sponsor and investigator may take appropriate urgent safety measures (USM) to protect a research participant from an immediate hazard to their health and safety. This USM can be taken before seeking approval from the competent authorities and ethics committee.

The main research ethics committee must be notified by email within three days. Information should include that such measures have been taken and the reasons why. The Sponsor will then follow-up with written notification within three days of the action being taken, i.e. in the form of an amendment, describing the event, the measures taken and justification for the measures taken. Where the USM requires an amendment to study documentation, this should be submitted as a substantial amendment as soon as possible and marked as being in response to USM. A copy of the USM notification should be submitted with the amendment.

If the Principal Investigator (and not the Sponsor) has instigated the USM, the Sponsor should be notified immediately so that they can assess and report the USM within the timelines required.

NHS R&D offices will require notification in accordance with local policies/procedures. Where applicable, oversight committees (such as the DMC) should review information relating to USM and report any recommendations to all relevant parties. The funder should be updated on all developments and actions as soon as possible.

8 DATA MANAGEMENT

8.1 Data collection

8.1.1 Data Sources

A full list of source data and location will be maintained in the Data Management Plan (DMP). Data extracted from GP records and sent to the central research team such as healthcare use, will also form part of the source data for this trial.

Data will be collected using electronic/paper case report forms (CRFs). Direct data entry to eCRFs will be done using REDCap. If paper CRFs are used these will be entered into the database as soon as possible.

Baseline consent will be documented using online or paper consent forms, and verbal consent will be taken (and audio-recorded) for qualitative interviews, with a consent form signed by the researcher on the participants behalf.

Screening, baseline, and follow-up data will be collated using validated and bespoke electronic and paper questionnaires. Where trial data has been collected on paper questionnaires, these questionnaires will be considered primary source documents, and data will be entered into the REDCap database by trial staff. Similarly, where patients or researchers have entered data directly onto electronic questionnaires, this will be saved directly to the REDCap database, and will be source data. Any paper copies will be stored in a secure locked cabinet in an access-controlled area.

Therapy data such as types of events worked on in therapy, depression scores, SUDs scores and scores on the VOC scale will be collected during EMDR sessions and recorded on the database as clinical data. Where consent is given, these data will be used for research purposes.

Audio recordings of therapy sessions will be deleted at the end of the study once the independent assessment of fidelity of the intervention has been completed.

Audio recordings of qualitative interviews will be deleted at the end of the trial, after being used to check the accuracy of interview transcripts and post analysis. All transcripts will be anonymised and stored for potential future use.

At the end of the follow-up period, health care resource data will be collected from patients' primary care notes. This data will either be captured electronically, or transcribed from care notes onto bespoke CRFs, prior to being entered into the study database.

The trial databases will incorporate data entry and validation rules to reduce data entry errors, and management functions to facilitate auditing and data quality assurance.

8.1.2 Data System

REDCap will be used to capture and store study data for the trial. REDCap is a web-based electronic central data management system which is built and supplied by Vanderbilt.

The BTC systems team have standard operating procedures (SOPs) to ensure there is a structured approach to designing, building, testing and validating the database prior to release.

Access to the trial REDCap database is managed at an individual level via delegation logs and requires a password that must meet the minimum format requirements.

Participant personal identifiers will be stored securely. Participants will be informed of data storage and security processes in the Patient Information Leaflet.

The database contains audit trails to record all changes to the data and who actioned the changes, user permissions and when access was granted and revoked. The database is held on UoB servers that are automatically backed up daily by UoB IT and stored securely.

In the event of a study amendment, updates to the study database will be coordinated through changes to the relevant specification documents. Specification updates will be discussed between the study team (including the statistician) and the CI.

8.2 Data quality

Throughout the trial, data integrity, accuracy and completeness of data collection will be monitored and reported in compliance with good clinical practice (GCP) guidelines. This may include source data verification, use of automated data validation rules, data cleaning, training and risk-based monitoring (further details of which can be found in section 9.2). Periodic data reviews will be carried out and audit trails will be maintained.

Qualitative data transcripts will be checked for accuracy using the audio-recordings.

8.3 Essential document storage and security

Essential documentation, as specified by the Sponsor, will be stored in an eTMF and eISF. Read only access to the relevant systems can be provided for inspection purposes.

Access to the eTMF and eISF will be restricted and access will be approved and monitored by the BTC trial team. All systems where essential documentation is held are automatically backed up daily by UoB IT teams and stored securely.

8.4 Essential document archiving

Essential documentation, as specified by the sponsor, and source data (including REDCap database) will be kept for at least 10 years after the end of the trial. Documents will be kept at the University of Bristol and/or participating centres for this time. At the end of the archiving period, documents will be destroyed by confidential means. All non-essential documentation will be destroyed securely prior to archiving.

Where trial data are stored in a paper format, these records will be identified by a label bearing the name and duration of the trial and clearly stating the 'do not destroy before' date. Where electronic records are in use, local centre policy will be followed.

Participant personal identifiers will be archived where they form part of the essential documentation and will be destroyed at the end of the archiving period.

A study archiving plan will be developed, to include the TMF and ISF, in accordance with the BTC archiving procedure which require Sponsor and CI oversight. Centres will retain access to their ISF throughout the archiving period and the trial archive will be available for inspection purposes.

Data held at the University of Bristol will conform to the University of Bristol Data Security Policy and be held in compliance with the UK General Data Protection Regulation (GDPR), tailored by the Data Protection Act 2018. All centres should send all consent forms, paper questionnaires and other trial documentation to the University of Bristol at the end of the trial, for central archiving.

